Although widely available, many people find regulated patient information leaflets unhelpful because they do not meet people's information needs – particularly their need to understand how well a medicine works.^{1–3} In order to make informed, evidence-based decisions aligned with their preferences, patients need clear information about the potential benefits, harms, and uncertainties of drugs, including treatment alternatives.^{3,4} However, much of this information is either inadequately communicated or entirely absent from current patient leaflets. Leaflets often omit the goal of treatment (e.g., whether the treatment is palliative or curative) and provide no data on the magnitude and relevance of expected benefits.⁵ While side effects are listed, they are rarely accompanied by data on frequency, severity,^{6–8} or how these risks compare to other treatments.

Patients consistently express interest in receiving written information about prescription drugs at the point of care that more effectively addresses their informational needs.^{1,2} The European Medicines Agency (EMA) recently proposed a series of reforms aimed at improving the clarity and usefulness of patient information leaflets. One key proposal is the introduction of a 'key information section'; a concise summary at the beginning of the leaflet that includes qualitative statements about the goal of treatment, main benefits, contraindications, and the most serious side effects.⁹

To inform the EMA's consultation on improving patient information leaflets, we developed a key information section that summarizes the main benefits and harms of a medicine. Its design was informed by evidence on effective health communication. Recognising that qualitative statements alone could be misinterpreted by patients,^{4,8,10} we incorporated a structured summary table presenting quantitative information on treatment effects and side effects. Previous research shows that patients not only want this type of information,^{1,2} but they also understand it, and can use it to make more informed decisions.^{4,11–13}

To evaluate the impact of structured benefit-harm information in patient leaflets, we will conduct a randomized controlled trial with a nationally representative sample of adults in the United Kingdom (UK). The trial will evaluate whether including qualitative or quantitative information about drug benefits and harms improves individuals' expectations and understanding of a newly approved drug. Participants will be randomly assigned to one of three groups: (1) the standard patient information leaflet (control), (2) a leaflet incorporating the EMA's proposed key information section with qualitative statements, or (3) a leaflet with a key information section that includes both qualitative and quantitative information on the drug's benefits and harms.

Methods

This study received ethics approval from the London School of Economics and Political Science. The protocol was registered prior to recruiting participants (ClinicalTrials.gov) and the study will be reported in accordance with the CONSORT guidelines for randomized controlled trials.

Randomization

Participants will be individually randomized with equal allocation to 1 of 3 versions of a patient information leaflet: (1) the standard patient information leaflet (control), (2) a leaflet incorporating the EMA's proposed key information section with qualitative statements, or (3) a leaflet featuring a key information section that summarises quantitative data on the drug's main benefits and harms in addition to qualitative statements. We will use Qualtrics to randomize participants and to administer the survey.

Participants

Adults 18 years and older, fluent in English, and residing in the UK will be invited to participate in this survey. Participants will be recruited by Cint, a market research company that identifies participants from hundreds of research panel providers that use different methods for recruitment. We plan to recruit a nationally representative census-matched sample of adults according to age, sex, and education. Informed consent will be obtained from participants before initiating the survey; participants will be directly compensated by the survey company after completion. No identifying information about participants will be recorded.

Interventions

Participants in the control group will receive the standard patient information leaflet for a recently approved cancer drug, obtained electronically from the EMA website. There are 2 experimental conditions.

For participants randomized to receive the EMA's proposed key information section with qualitative statements, we developed a version based on the draft proposal published by the EMA.⁹ The proposed key information section summarizes the goal of treatment, main benefits, contraindications, and most serious side effects. To ensure accuracy of our interpretation, we sought feedback from the EMA. The final version tested in the trial incorporated their suggestions.

Next, we developed a key information section that includes quantitative data on the drug's main benefits and side effects, modeled on the Drug Facts Box – a tabular summary format for prescription drugs, designed to resemble a nutrition label.¹³ The key information section presents qualitative information about the drug (including its indication and treatment goal), and how it was studied (the comparator treatment and number of patients enrolled in the clinical trial that supported the drug's approval). It supplements this with quantitative data the drug's benefits and side effects. Data on the drug's benefits and side effects were sourced from European Public Assessment Reports (EPARs). Further details are provided in the appendix.

Procedure

Upon entering the study, participants will be randomized to 1 of 3 versions of a patient leaflet. The patient leaflet is for tivozanib (Fotivda), a cancer drug approved by the EMA for the treatment of advanced kidney cancer. An electronic version of the patient leaflet along with a download link will be displayed alongside each multiple-choice question. Participants will first complete a practice question designed to test their ability to scroll through and navigate the leaflet. Participants who answer the practice question incorrectly will be excluded from the study at this stage.

The first set of questions is designed to evaluate participants' expectations, perceived magnitude, and understanding of the drug's benefits and side effects based on the information provided in the patient leaflet. To assess expectations, we will ask participants about the likelihood that patients with advanced kidney cancer would be cured, live longer, or

feel better if they were treated with tivozanib. They will also be asked about the perceived magnitude of the tivozanib's benefits and side effects.^{13–15}

To assess understanding, we will ask participants 3 questions: (1) the approved indication of tivozanib, (2) the most common serious side effect associated with treatment, and (3) the recommended dose of treatment. Answers to all 3 questions can be found in the standard patient leaflet. Information about the drug's indication is also included in both key information sections; information about the most common serious side effect is presented in the EMA's proposed key information section with qualitative statements. Participants randomized to the key information section with both qualitative statements and quantitative data will receive 2 additional questions: one asking them to identify the difference in overall survival between tivozanib and standard treatment, and another asking about the difference in serious side effects.

Next, all participants will be asked a series of questions to assess their satisfaction with the information presented in the version of the patient leaflet they were assigned. Before ending the survey, we will ask participants for information about their demographics: their age, sex, highest level of educational attainment, and personal experience with cancer (whether themselves, an immediate family member or close friend had been diagnosed with cancer).

Primary outcome

The primary outcome of the study is participants' expectations about the drug's benefits and side effects. We selected tivozanib as the test treatment because it is representative of many recently approved cancer drugs. Tivozanib is not curative for advanced kidney cancer and, at the time of approval, it demonstrated no additional overall survival or quality of life benefit relative to standard treatment (sorafenib). Owing to the lack of information about drug benefits in the standard patient leaflet and the limited information quantifying side effects, we hypothesized that participants would overestimate the benefits and underestimate the side effects of tivozanib.¹⁴

We assessed 3 questions related to participants' expectations about treatment outcomes: whether participants expected that tivozanib was curative, extended overall survival, or improved quality of life. We selected these 3 outcomes because research shows that patients undergoing cancer treatment value these outcomes the most.^{15,16} For the primary analysis, we will compare the proportion of participants in each group who had accurate expectations for at least 2 of the 3 treatment outcomes with tivozanib (defined as responding "definitely no" or "probably no" to these questions).

Secondary outcomes

Participants' understanding of the information presented in the patient leaflet, their perceived magnitude of the drug's benefits and harms, and their satisfaction with the information are secondary outcomes of the trial. To assess understanding, we will compare the proportion of correct responses to each comprehension question across the randomized groups. To assess participants' perceived magnitude of the drug's benefits and harms, we will compare the proportion of participants in each group who responded that (1) the benefits of tivozanib were large, (2) the side effects were not concerning, and (3) the benefits of tivozanib outweighed the side effects. To assess satisfaction, we will compare the proportion of participants in each group who provided positive ratings about the leaflet (e.g., reporting that the leaflet was helpful and easy to understand).

Quality control

We will use several strategies to enhance the reliability and validity of the survey response data. First, we have included 2 attention check questions at different points throughout the survey. The first question will validate that participants can navigate the online survey and scroll through the patient leaflet; the second question will ask participants to select a specific

answer to ensure that they are paying attention. Participants that answer either question incorrectly will be excluded from the study at that stage. We will also exclude participants that (1) do not complete the survey, (2) complete the survey but straight-line their responses, and (3) participants that complete the survey in under 180 seconds.

Statistical analysis

The sample size and power calculations for this trial were informed by previous studies.¹³ This trial is powered to detect an absolute difference of 10% between groups (60% vs 50%) with 90% power and a two-sided alpha of 0.05. We plan to adjust for 3 pairwise comparisons for the primary outcome, comparing each of the intervention arms with one another. Therefore, we aimed to recruit 700 participants per group and considered Bonferroni-corrected p values <0.0167 to be statistically significant.

We will use χ^2 tests to compare the difference in proportions between groups. Logistic regression models will be used for adjusted analyses, controlling for participant demographics. We will conduct additional subgroup analyses to explore heterogeneity of treatment effects based on participants' sex, age, education level, and personal experience with cancer.

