- If you get any side effects, talk to your doctor, pharmacist or nurse. This includes any possible side effects not listed in this leaflet. See section 4.

What is in this leaflet

1. What Fotivda is and what it is used for
2. What you need to know before you take Fotivda
3. How to take Fotivda
4. Possible side effects
5. How to store Fotivda
6. Contents of the pack and other information

1. What Fotivda is and what it is used for

The active substance in Fotivda is tivozanib, which is a protein kinase inhibitor. Tivozanib reduces the supply of blood to the cancer, which slows down the growth and spread of cancer cells. It works by blocking the action of a protein called vascular endothelial growth factor (VEGF). Blocking the action of VEGF prevents the formation of new blood vessels.

Fotivda is used to treat adults with advanced kidney cancer. It is used where other treatments such as interferon-alpha or interleukin-2 have either not yet been used or have not helped to stop your disease.

2. What you need to know before you take Fotivda

Do not take Fotivda:

- If you are allergic to tivozanib or any of the other ingredients of this medicine (listed in section 6);
- If you are taking St. John's Wort (also known as *Hypericum perforatum*, a herbal remedy used for treatment of depression and anxiety).

Warnings and precautions

Talk to your doctor, pharmacist or nurse before taking Fotivda:

- if you have **high blood pressure**
Fotivda can increase your blood pressure. Your doctor will monitor your blood pressure regularly and, if it is too high, may either give you a medicine to lower it, or reduce your dose of Fotivda. However, if your blood pressure remains too high, your doctor may decide to interrupt or to stop treatment with Fotivda. If you are already taking a medicine to treat high blood pressure, and your doctor reduces the dose of Fotivda or interrupts or stops treatment, you will be regularly checked for low blood pressure.
- if you have or have had an aneurysm (enlargement and weakening of a blood vessel wall) or a tear in a blood vessel wall.

KEY INFORMATION

What is Fotivda and what it is used for

- Fotivda is a medicine for treating adults with advanced kidney cancer. Fotivda may be used in previously untreated patients or in those whose disease has got worse despite treatment with another medicine that works in a different way.
- Fotivda does not cure advanced kidney cancer.

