- Fotivda may increase how long people live without their disease getting worse. However, it does not cure advanced kidney cancer.

For further information about Fotivda and its uses, see section 1.

What you need to know before you take Fotivda

- Do not take Fotivda if you are allergic to the active ingredient, tivozanib, or if you are taking St. John's Wort (a herbal remedy for depression).
- Talk to your doctor if you have high blood pressure, have had an aneurysm (a bulge in a blood vessel), have had blood clots or have any of the signs or symptoms of heart failure.

For further information, see section 2.

Most important side effects with Fotivda

- The most common side effect with Fotivda is high blood pressure (which occurs in almost half of patients and can be serious in a quarter of patients).
- Other common side effects are voice changes, tiredness and diarrhoea (which occur in about a quarter of patients).

For the full list of possible side effects, see section 4.

To understand all information about using this medicine, it is very important that you read the rest of this leaflet.

Key information about Fotivda for renal cell carcinoma (kidney cancer)

What is Fotivda and what is it used for:

- Fotivda (tivozanib) is a medicine to treat adults with advanced kidney cancer that has come back after previous treatment or has spread to another part of the body.
- Fotivda does not cure advanced kidney cancer.
- Fotivda may increase the time until a test shows the cancer has grown or spread, but it has not been shown to extend how long people live.

Benefits and side effects of Fotivda:
 In a study involving 517 people, Fotivda was compared to sorafenib, a standard treatment for kidney cancer. What difference did Fotivda make?

	Fotivda	Standard treatment
How long did people live?	People given Fotivda lived 2.6 months less . However, this finding may be due to chance.	28.2 months vs 30.8 months
How did people feel?	People given Fotivda felt 1.1 points worse on a 108-point scale. However, this finding may be due to chance	4.8 points worse vs 3.7 points worse
How long did people have before the cancer grew or spread?	People given Fotivda had 2.8 months longer before the cancer grew or spread.	11.9 months vs 9.1 months
How common were serious side effects?	People given Fotivda had 6% fewer serious side effects (disabling, life-threatening, or requiring hospitalization).	64% vs 70%

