Note: Left panel shows the standard patient leaflet for tivozanib (control); upper right panel shows the EMA's proposed key information section with qualitative statements; lower right panel shows the key information section containing both qualitative and quantitative information.

----- end of page-----

Section A: Previous experience using the patient leaflet

1. If you are currently prescribed or have ever been prescribed a medicine, how often do you read the patient leaflet?
 - Often
 - Sometimes
 - Rarely
 - Never
2. If you are currently prescribed or have ever been prescribed a medicine, how often do you talk to your doctor about the information you see in the patient leaflet?
 - Often
 - Sometimes
 - Rarely
 - Never

----- end of page-----

Section B: Participants' expectations and understanding of treatment using the patient leaflet

Imagine that your doctor prescribes you a new medicine. When you pick up the medicine from the pharmacy, you read the patient leaflet included in the box.

This patient leaflet is for a medicine called Fotivda. You can zoom in and scroll through every page of the leaflet. You can also download it here: [Fotivda.pdf](#)

You will be shown the patient leaflet for Fotivda on every page for the next few questions, along with an option to download the leaflet. Please use the information in the leaflet to answer the questions.

----- end of page-----

3. This first question is practice. Scroll to section 3 of the leaflet and find the first word.
 - Always **[correct]**
 - Serious
 - Patient
 - Chance

----- end of page-----

4. What is Fotivda used for?
 - To treat adults with breast cancer
 - To treat adults with heart failure
 - To treat adults with advanced kidney cancer **[correct]**
 - To treat adults with advanced lung cancer
 - Not sure

----- end of page-----

5. Does Fotivda cure advanced kidney cancer?
 - Definitely yes
 - Probably yes
 - Probably no
 - Definitely no

----- end of page-----

6. Do people with advanced kidney cancer live longer when treated with Fotivda?
 - Definitely yes
 - Probably yes
 - Probably no
 - Definitely no

----- end of page-----

7. Do people with advanced kidney cancer feel better when treated with Fotivda?

- Definitely yes
- Probably yes
- Probably no
- Definitely no

----- end of page-----

8. Compared to standard treatment, how long did people given Fotivda live? **[Key information table group]**

- 6 months **less** than people given standard treatment

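### All three primary items are scored accurate on 'no', so the randomized comparisons cannot separate more accurate expectations from general negativity induced by a leaflet version

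*Combined protocol and SAP*

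**What the plan says.** Under Primary outcome, three expectations are assessed: "whether participants expected that tivozanib was curative, extended overall survival, or improved quality of life". The analysis compares the proportion with "accurate expectations for at least 2 of the 3 treatment outcomes with tivozanib", and an accurate answer means "responding 'definitely no' or 'probably no' to these questions".

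The survey items are Q5 ("Does Fotivda cure advanced kidney cancer"), Q6 ("Do people with advanced kidney cancer live longer when treated with Fotivda") and Q7 (whether patients feel better). All three use the same four-point scale from definite yes to definite no, with no 'not sure' option.

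All three leaflet versions in Figure 1 carry text on slowed progression. The control leaflet says the drug reduces blood supply to the cancer, "which slows down the growth and spread of cancer cells". The qualitative section says it may lengthen the time without worsening disease. The quantitative section says "Fotivda may increase the time until a test shows the cancer has grown or spread" and gives a 2.8-month difference in its table. No survey question asks about this.

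Q8 (difference in survival) and Q11 (difference in serious side effects) go to the quantitative group only.

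**The concern.** A respondent who says 'no' to everything scores three of three. A habit of saying 'no' that people bring to the survey is balanced by randomization. Negativity caused by reading one version is not: it is a consequence of allocation, and the endpoint counts it as accuracy.

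The versions differ in ways that make this conceivable. Only the quantitative section reports shorter survival (2.6 months) and worse quality of life (1.1 points). The qualitative section states twice that the drug does not cure and, as shown in Figure 1, says nothing about overall survival or quality of life. Success in that group still needs at least one 'no' on Q6 or Q7, which its key information section does not directly supply.

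The claim the trial hopes to make is that a key information section improves expectations. With every primary item keyed the same way, no planned comparison would show whether readers had also come to reject a benefit that the leaflet reports.

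**Working it through.** **Inputs.** The scoring rule and the two-of-three threshold are under Primary outcome. The 50% and 60% rates, 90% power, alpha of 0.0167 and 700 per group are under Statistical analysis. The documents give no item-level rates and no correlation between items, so those are assumed below.

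**1. The plan's own figure.** n = [z(α/2)·√(2p̄(1−p̄)) + z(β)·√(p₁(1−p₁)+p₂(1−p₂))]² / Δ², with p₁ = 0.50, p₂ = 0.60, p̄ = 0.55, two-sided α = 0.0167 and 90% power. This gives 667 per group, or 686 with a continuity correction. Power at 700 is 91.5%. The planned 700 is consistent, and the sample size is not in dispute.

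**2. Which questions could separate the two explanations?**

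| Items | Asked of | Accurate answer | Separates accuracy from negativity? |
|---|---|---|---|
| Q5–Q7 | all | 'no' on each | no |
| Q4, Q12, Q15 | all | indication, side effect, dose | no, not about benefit |
| Q9, Q13, Q14 | all | none keyed | no, lower ratings fit either explanation |
| Q8 | quantitative group | 2.6 months shorter | partly, since a wrong option (6 months shorter) is more pessimistic |
| Q11 | quantitative group | 6% less common | in principle, since it is keyed in the drug's favour |

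Q8 and Q11 have no counterpart in the other groups, and no analysis links them to Q5–Q7. Q11 has a further difficulty. The Appendix, under Drug information, says severe harms were more common with tivozanib (70% against 64%). The Figure 1 table and the Q11 key say they were 6% less common (64% against 70%). These places must be reconciled before Q11 can be read at all.

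The straight-lining exclusion under Quality control is not defined, so it cannot be assumed to remove all-'no' respondents. Three 'no' answers on Q5–Q7 are also the perfect score.

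**3. How much negativity would imitate the planned effect?**

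- *Independent items, common rate p.* P(at least 2 of 3) = 3p² − 2p³. At p = 0.500 this is 0.750 − 0.250 = 0.50. At p = 0.567 it is 0.964 − 0.365 = 0.60. The shift is 6.7 points per item.
- *Fully correlated items.* P = p, so the shift is 10 points per item.
- *A share f of a group switches to all 'no', regardless of how they would otherwise have answered.* The rate becomes p + f(1−p). At p = 0.50 and f = 0.20 it is 0.50 + 0.20 × 0.50 = 0.60. For baseline success of 30%, 40%, 50% and 60%, the f that adds 10 points is 0.10/(1−p), or 14%, 17%, 20% and 25%.

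With 700 per group, α = 0.0167 and a 50% baseline, a switch of 10% (rate 55%), 15% (57.5%) or 20% (60%) would be declared significant with probability about 30%, 66% and 91.5%. The smallest observed difference that reaches significance is about 6.4 points, equivalent to f = 0.064/0.50 ≈ 13%.

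**4. Would a 'yes'-keyed item respond?** Suppose a share q answers it accurately, with q assumed to lie between 50% and 80%. If 20% switch to all 'no', accuracy falls to 0.8q: from 50% to 40%, or from 80% to 64%, a drop of 10 to 16 points. The widest 95% half-width for a difference at 700 per group is 1.96 × √(2 × 0.25/700) = 0.052, or 5.2 points. A shift of that size would be visible.

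**The case against.** The strongest case on the other side has four parts.

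- **The endpoint fits its hypothesis.** The primary outcome is expectations, and understanding is a separate secondary outcome. The stated hypothesis is that readers overestimate benefit, and the three outcomes were chosen because patients value them most. Correcting overestimation must move answers towards 'no'. This stands, and it is why the primary endpoint should be kept. It does not explain why there is no item on which general negativity and accuracy point in opposite directions.
- **The quantitative section answers two items directly.** It says the drug is not curative and that longer survival has not been shown. That settles Q5 and Q6 and meets the two-of-three rule, with the leaflet displayed beside each question. This also stands. A gain in that group has a legitimate route, but the composite would look the same under the other route.
- **The quantitative table is not uniformly negative.** It has two favourable rows (progression and serious side effects), and both unfavourable rows carry a caveat about chance. This stands: nothing in the documents shows that any version induces general negativity.
- **A 'yes'-keyed item has the mirror-image weakness.** Over-optimistic readers would score well by saying 'yes' throughout. This stands, especially for the control leaflet, which supports the answer only through a statement of mechanism. The item is therefore useful beside Q5–Q7, not alone.

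A reader might infer that the trial has no means at all of telling accuracy from pessimism. The documents do not support that. In the quantitative group, Q8 and (once its figures are reconciled) Q11 allow a descriptive check, because a blanket pessimist would tend to miss both. What is missing is a randomized comparison.

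**Conclusion.** The concern holds in a limited form. Q5–Q7 are all keyed 'no', and no item given to every group has a favourable accurate answer about benefit. The primary comparison and the other between-group comparisons therefore cannot distinguish more accurate expectations from negativity caused by a version.

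The figures in the working show vulnerability only. They rest on the planned 50% baseline, on assumed dependence between items (independence for 6.7 points, full correlation for 10) and, for the 20% figure, on switchers being unrelated to how they would otherwise have answered. A reader might infer that an observed gain would be spurious. The documents do not support that either: they contain no evidence that induced negativity will occur, and the quantitative section offers a direct route to correct answers.

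The endpoint and sample size need no change. The gap is in interpretation and is cheap to close.

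**What to change.** Keep the primary endpoint and the 700 per group. Add one question to all groups, with the same four options as Q5–Q7, asking whether people treated with Fotivda go longer before their cancer grows or spreads. Score definite or probable 'yes' as accurate. Place it after Q14 so that it does not prime the ratings in Q9 and Q14.

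Report it by group as a secondary outcome, with confidence intervals for the pairwise differences, beside Q5, Q6 and Q7 shown separately. Do not use it as a pass/fail gate: if true accuracy were equal, chance alone would produce an observed fall about half the time. If the composite rises while accuracy on this item drops materially, describe the primary result as fewer over-optimistic expectations and not as improved accuracy.

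Reconcile the side-effect figures in the Appendix (Drug information), the Figure 1 table and the Q11 key.

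If the survey has already been fielded, report Q5–Q7 by item and group, cross-tabulate Q8 with the primary outcome in the quantitative group, and limit the accuracy claim accordingly.

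**Cost.** A few seconds per participant, three more secondary pairwise comparisons, and careful reading of the control group, where the leaflet gives only a mechanism and over-optimistic respondents would also answer 'yes'.

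### Does comparing the two key information sections on the 2-of-3 composite need item results, an attribution limit and a stated comparator before it can be interpreted?

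*Combined protocol and SAP*

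**What the plan says.** Under Methods, Primary outcome, each participant is scored on survey questions 5 (cure), 6 (longer life) and 7 (feeling better). A definite or probable no counts as accurate, and the primary analysis compares the proportion "who had accurate expectations for at least 2 of the 3 treatment outcomes with tivozanib". Under Statistical analysis, all three pairs of groups are tested at a Bonferroni level of 0.0167, so the quantitative section against the qualitative section is one of three primary tests.

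Under Secondary outcomes the plan states: "To assess understanding, we will compare the proportion of correct responses to each comprehension question across the randomized groups". Those items cover indication, the most common serious side effect and dose, with two more for the quantitative group. Nothing similar is written for questions 5 to 7.

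The tested texts are in Figure 1. The quantitative section's third bullet ends "but it has not been shown to extend how long people live", and its table repeats the survival result: "People given Fotivda lived 2.6 months less". The matching bullet in the qualitative section reads "Fotivda may increase how long people live without their disease getting worse", which concerns progression and not overall survival. Quality of life appears only in the quantitative section's table: "People given Fotivda felt 1.1 points worse on a 108-point scale", with group values "4.8 points worse vs 3.7 points worse".

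The Primary outcome section gives the reason for scoring no as accurate on survival and quality of life: at approval, "it demonstrated no additional overall survival or quality of life benefit relative to standard treatment (sorafenib").

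**The concern.** Three things look unsafe.

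- **Attribution.** The introduction frames the aim as the effect of qualitative or quantitative information, and the third group is described as receiving data on top of qualitative statements. A reader may take the contrast between the two key information sections as the effect of adding numbers. But the verbal content also differs, and it differs on question 6, which is scored in the endpoint.
- **No item results.** With only the composite planned, a significant difference would not show whether expectations about cure, survival or quality of life had moved.
- **Scoring reference.** Questions 6 and 7 name no comparator, while the scoring rests on evidence against sorafenib. Someone who answers yes and means compared with no treatment is counted as inaccurate.

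At stake is the wording of the conclusion from one of three alpha-controlled comparisons, and the meaning of accurate on two of its three items.

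**Working it through.** **1. The plan's own figure.** Inputs from Statistical analysis: 60% vs 50%, 90% power, two-sided alpha 0.05/3 = 0.0167, so z = 2.394 for alpha and 1.282 for power. The pooled-variance formula gives

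n = [2.394·√(2·0.55·0.45) + 1.282·√(0.5·0.5 + 0.6·0.4)]² / 0.10² = 667 per group,

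or 687 with a continuity correction, against 700 planned. Power at 700 is 91.5%. The design reproduces, and nothing in the concern alters it.

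**2. What each text offers on each item** (from Figure 1; the full leaflet is not reproduced there).

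| Item | Standard leaflet, part shown | Qualitative section | Quantitative section |
|---|---|---|---|
| 5, cure | not addressed | bullets: not a cure | bullet: not a cure |
| 6, longer life | not addressed | progression only | bullet and table row |
| 7, feeling better | not addressed | not addressed | table row only, words and numbers mixed |

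The quantitative section also adds a short trial description, and it lacks the qualitative section's contraindications, precautions and named side effects. The contrast is therefore one format against another. The plan describes it that way: Randomization and Interventions define the third group as a combined package, and the Appendix presents the third bullet as a deliberate design element.

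**3. What the composite can show.** A 2-of-3 composite puts no bound on any single item. At a composite of 60%, the question 7 rate can be 0% (60% of participants accurate on 5 and 6 only, the rest on at most one of those two). It can also be 100% (60% accurate on 7 plus one other item, the rest on 7 only). The full 10-point design difference arises if question 5 is 100% and question 7 is 0% in both groups, with question 6 at 50% vs 60%. A less extreme case uses assumed rates and independent items, for which the composite is ab + ac + bc − 2abc. With question 5 at 85% and questions 6 and 7 at 34.2%, the composite is 50%. Raising either 6 or 7 alone to 50.6% brings it to 60%. This holds for any 2-of-3 endpoint. It says nothing about the likely pattern here, and nothing about words versus numbers.

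**4. What item results would add.** The half-width of a 98.33% interval for a pairwise difference is 2.394·√[(p₁(1−p₁) + p₂(1−p₂))/n].

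- n = 700, 50% vs 50%: 2.394·√(0.50/700) = 6.4 points, the worst case.
- n = 700, 80% vs 90%: 2.394·√(0.25/700) = 4.5 points.
- n = 560, an assumed 20% loss to the Quality control exclusions, 50% vs 50%: 2.394·√(0.50/560) = 7.2 points.

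Three items by three pairs make nine intervals. The 98.33% level covers three comparisons, not nine, so these would be descriptive. They need no new data. Because question 6 is answered by both a bullet and a table row, and question 7 by a row that mixes words and numbers, they would still not isolate the numbers.

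**5. The comparator.** Participants are told at the start of survey Section B to answer from the leaflet, and Procedure describes the questions in the same terms. In the text shown, no group is given evidence of longer life or feeling better compared with no treatment. The survival bullet in the quantitative section names no comparator. A yes is therefore unsupported by what the participant was given to read, whichever comparator they had in mind. On question 7, the table also shows a decline within the tivozanib group. The share of participants who would read the questions as compared with no treatment cannot be estimated from the documents.

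**The case for a change.** The best case for a change is that one paragraph would cost almost nothing. Specifying item results in advance guards against selective emphasis, and the plan already does so for the comprehension questions. The introduction's wording invites a conclusion about numbers that the two texts cannot support. The comparator is visible to only one group, since the text shown for the other two names no trial comparator.

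Much of this is factually right. Questions 5 to 7 appear only inside the composite, no limit on attribution is written, and the consequence of the sorafenib basis for scoring is not spelled out. Reporting the three items by group, and describing the result as format versus format, would be good practice.

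It does not amount to a fault in the plan. The attribution caveat guards against a claim the plan does not make. The item table is ordinary descriptive reporting and would not resolve the question of words versus numbers. Defining accurate as relative to standard treatment would be a step backwards: the plan defines it by the response given, and the new definition would rest on a reference that two groups were not shown. Rewording questions 6 and 7 is a trade-off, because it would alter the lay expectation being measured and echo the quantitative section's table.

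**Conclusion.** No change to the plan is needed. The comparison of the two key information sections is a valid randomized contrast of whole formats, and the composite answers the question put to it. The sample size (667 to 687 by calculation, 700 planned), alpha and primary test are untouched. What remains is reporting detail that analysts can supply sensibly: questions 5, 6 and 7 by group as descriptive results, and a conclusion worded as one format against another. The discussion may note that the scoring of questions 6 and 7 rests on evidence against sorafenib while the questions name no comparator. The endpoint should not be redefined.

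This rests on three conditions. The ±6.4-point bound assumes 700 analysed per group. The reading of the leaflets relies on the text reproduced in Figure 1. Valid here refers to the randomized contrast of formats; whether the post-randomization exclusions under Quality control fall evenly across groups is a separate matter.
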